### **Randomization of the Study Patients**

In order to assign patients to specific treatment groups in an unbiased manner, randomization will occur prior to surgery. After the patient has met the entrance criteria, and given full informed consent to participate in the study, they will be assigned to the treatment group. The randomization will be stratified by variables with potential confounding effects on the outcomes of interest. Specifically, patients will be stratified by gender (male / female), Body Mass Index category (<25.0 / 25.0-29.9 / ≥30) and age group (21-55 / 56-85). Within each stratum, subjects will be assigned to one of the two treatment groups using a computerized dynamic allocation program. Patient randomization will be performed just prior to surgery.

# Sample Size/Inclusion Criteria

Five hundred seventy-two (572) patients will be recruited into the study; 286 receiving N2Vac polyethylene and 286 receiving X3 polyethylene.

### **Surgical Technique**

All procedures will be performed by one of nine knee arthroplasty surgeons ([name]). The femoral, tibial and patellar components will be cemented. The patellar components will be all-polyethylene.

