## Hospitalization

Patients will be admitted to the hospital on the day of their surgery, unless medical problems dictate earlier admission. Hospitalization of 3 to 5 days is routine for these

patients, although complications may prolong this. These will be recorded on the data collection forms. An extension splint will not be used following surgery and no pillows are to be used under the knee. Continuous passive motion will be used according to the individual surgeon's discretion as part of the postoperative management. The patient will receive one preoperative dose and two postoperative doses of IV antibiotics separated by a 6 to 8 hour period. All patients will receive appropriate anticoagulation for deep venous thrombosis prophylaxis at the individual surgeon's discretion.

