# **Post-Op Physical Therapy**

Both treatment groups will have similar postoperative care. Structural physical therapy will begin the day after surgery and continued during the hospitalization. A home therapy program will be given to the patient.

- a. Initial Post-op Day 1, use of walker or personnel to assist with transfer from bed to chair.
- b. Active ROM to begin within first 24 hours postop.
- c. Weight bearing status and progression as tolerated.

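### Operating surgeon is in neither the allocation nor any named analysis; a surgeon term would add modest precision for ROM and the other continuous outcomes, and no bias is at stake

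*Combined protocol and SAP*

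**What the plan says.** - **Surgeons.** Surgical Technique: "All procedures will be performed by one of nine knee arthroplasty surgeons".
- **Discretionary care.** Hospitalization: "Continuous passive motion will be used according to the individual surgeon's discretion as part of the postoperative management", and "All patients will receive appropriate anticoagulation for deep venous thrombosis prophylaxis at the individual surgeon's discretion". The Progression section repeats the discretion for CPM and ends CPM at hospital dismissal. Post-Op Physical Therapy adds: "Both treatment groups will have similar postoperative care".
- **Allocation.** Randomization of the Study Patients gives the criterion: "The randomization will be stratified by variables with potential confounding effects on the outcomes of interest". It then names gender, three BMI classes and two age groups, and continues: "Within each stratum, subjects will be assigned to one of the two treatment groups using a computerized dynamic allocation program". Surgeon is not named.
- **Analysis.** Efficacy Analyses gives a Poisson rate ratio with a 95% interval for revision, and t-based intervals on mean differences for the continuous secondary outcomes. Neither has a covariate. The Summary mentions generalized linear regression for Knee Society outcomes without naming covariates, and puts DVT and pulmonary embolus among the event-rate endpoints.
- **Blinding.** Study Design says that patients are blinded, and Study Procedures refers to a blinded research assistant for data collection. Surgeons are not said to be blinded.

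**The concern.** The plan sets its own test for a stratification factor: potential to confound the outcomes. Surgeon arguably meets it. Surgeon determines CPM use and prophylaxis, range of motion (ROM) is a secondary efficacy parameter, and DVT and pulmonary embolus are named endpoints. Nothing controls how each surgeon's patients divide between arms, and no analysis removes differences between surgeons.

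What is at stake is precision. If outcomes differ by surgeon, that variation stays in the error term of every comparison. For continuous outcomes measured in most patients, removing it narrows the interval at almost no cost.

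**Working it through.** **Plan's own figures.** Schoenfeld's formula for a ratio of 0.32, two-sided alpha 0.05, 80% power and 1:1 allocation gives (1.960 + 0.842)² / (0.25 × ln(0.32)²) = 24.2, so 25 revisions against the 26 in Sample Size Justification. Power at 26 is 0.83. Then 26 / 0.05 = 520 and 520 × 1.10 = 572, as stated.

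**Per-surgeon counts.** 572 / 9 = 63.6 patients and 26 / 9 = 2.9 revisions per surgeon. If allocation ignores surgeon, a surgeon with 64 cases has a 95% binomial range of 24 to 40 X3 cases. These imbalances partly cancel across nine surgeons, so the trial-level effect has to be computed directly.

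**Effect on the revision ratio.** Simulation with nine surgeons, 520 evaluable patients, 260 per arm allocated without regard to surgeon, mean 10-year risk 5%, true ratio 1, log-normal surgeon risks, and 20,000 replicates per row. The surgeon SDs are assumptions. Simple allocation stands in for the dynamic program, which also ignores surgeon. The last column divides the squared SD of the log factor by the sampling variance of the log ratio, 4 / 26 = 0.154.

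| Assumed SD of log risk between surgeons | 95% range of the factor on the ratio | SD of log factor | Share of sampling variance |
|---|---|---|---|
| 0.3 | 0.95 to 1.05 | 0.025 | 0.4% |
| 0.5 | 0.92 to 1.09 | 0.042 | 1.2% |
| 0.8 | 0.87 to 1.15 | 0.067 | 2.9% |
| 1.0 | 0.85 to 1.19 | 0.083 | 4.5% |

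The factor is centred on 1.00 in every row. A skewed caseload (25% down to 2% of cases per surgeon) gives nearly the same ranges. For scale, sampling error with 26 revisions puts the 95% limits a factor of exp(1.96 × √0.154) = 2.16 either side of the estimate.

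**Error rates.** Coverage of the unadjusted 95% interval at a true ratio of 1 is about 96% in every row. At a true ratio of 1.2, the chance of wrongly declaring non-inferiority is 1.9% with surgeon SD 0, 0.5 or 1.0 (40,000 replicates each).

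**Gain for continuous outcomes.** If surgeon explains a share ρ of the outcome variance, a surgeon term leaves 1 − ρ of it, which is worth 572 / (1 − ρ) − 572 extra patients:

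- ρ = 2%: 583.7 − 572, about 12
- ρ = 5%: 602.1 − 572, about 30
- ρ = 10%: 635.6 − 572, about 64

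Interval width shrinks by 1 − √(1 − ρ), that is by 1.0%, 2.5% and 5.1%. The values of ρ are assumptions, and the gain in patients falls in proportion when fewer have ROM measured.

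**Crossed strata.** 2 × 3 × 2 = 12 existing strata; 12 × 9 = 108 cells; 572 / 108 = 5.3 patients per cell.

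**The case against.** Balancing on patient factors and leaving surgeon to chance is a legitimate choice. Individual randomization makes surgeon, and the care each surgeon chooses, comparable between arms in expectation, and the ordinary interval covers chance differences. Similar care in both groups does not require an even split within each surgeon. This stands, and it limits the point to precision.

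A reader might infer that surgeon imbalance, with shifts of up to 1.09 or 1.15, threatens the 1.2 non-inferiority margin. The documents do not support that. The rule in Efficacy Analyses reads the upper confidence limit, not the point estimate, and that limit lies a factor of 2.16 above the estimate whatever the surgeons do. With 26 revisions and a true ratio of 1, power for non-inferiority is about 7%, and about 945 revisions would be needed for 80%. The event count limits that test.

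A reader might also infer that discretionary CPM distorts the ROM comparison. That link is weak: CPM ends at dismissal, and ROM is first tested at two years. The case for a surgeon term rests on surgeon differences in general, whose size the documents do not give.

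Changing the allocation also has a cost. The plan describes dynamic allocation within strata and does not say whether the program can take a marginal factor. Balancing by surgeon makes assignments more predictable to operators who are not said to be blinded. If knowing the insert led to different care by arm, balancing on surgeon would not cure it.

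**Conclusion.** The omission is real, and its consequence is minor. It produces no bias, no loss of coverage and no inflated type I error, and its effect on the revision ratio is negligible beside the sampling error. That holds for assumed between-surgeon SDs from 0.3 to 1.0. It does not depend on reaching 26 revisions: at the plan's own rates the expected count is 260 × 0.05 + 260 × 0.016 = 13 + 4.16 = 17.16, the sampling variance rises to 1/13 + 1/4.16 = 0.317, and the surgeon share falls further.

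What remains is a cheap precision gain for ROM and the other continuous secondary outcomes, equal to the share of variance that surgeon explains. The 2% to 10% used here is an assumption. No gain of any size should be claimed for revision.

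**What to change.** 1. **Continuous outcomes.** In Efficacy Analyses, replace the unadjusted t-based comparison of ROM and the other continuous secondary outcomes with a linear model that has treatment as a fixed effect and operating surgeon as a random effect. This also fits the regression that the Summary promises for Knee Society outcomes.
2. **Event outcomes.** Keep the unadjusted Poisson ratio as the primary analysis. Add a surgeon-stratified sensitivity analysis for DVT/PE and revision, such as a Mantel-Haenszel rate ratio. Do not use surgeon fixed effects: about three revisions per surgeon would make them unstable.
3. **Allocation, optional and only if enrolment is open.** Surgeon may be added as a marginal factor with a random element in the dynamic program, not crossed into 108 cells.

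The cost of items 1 and 2 is one extra model term and one sensitivity table, provided that operating surgeon is on the case report form. Item 3 costs a possible change to the algorithm, slightly looser balance on the existing factors and somewhat greater predictability. None of this touches the surgeons' discretion over CPM or prophylaxis.

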## Hospitalization

Patients will be admitted to the hospital on the day of their surgery, unless medical problems dictate earlier admission. Hospitalization of 3 to 5 days is routine for these

patients, although complications may prolong this. These will be recorded on the data collection forms. An extension splint will not be used following surgery and no pillows are to be used under the knee. Continuous passive motion will be used according to the individual surgeon's discretion as part of the postoperative management. The patient will receive one preoperative dose and two postoperative doses of IV antibiotics separated by a 6 to 8 hour period. All patients will receive appropriate anticoagulation for deep venous thrombosis prophylaxis at the individual surgeon's discretion.

# **Post-Op Physical Therapy**

Both treatment groups will have similar postoperative care. Structural physical therapy will begin the day after surgery and continued during the hospitalization. A home therapy program will be given to the patient.

- a. Initial Post-op Day 1, use of walker or personnel to assist with transfer from bed to chair.
- b. Active ROM to begin within first 24 hours postop.
- c. Weight bearing status and progression as tolerated.

### Progression

- Progress ambulation from walker or crutches to a cane as tolerated
- Post-Op Day 1 commence ice and exercises as per exercise attached. May include patellar mobilizations, massage to reduce swelling.
- CPM initiated (at the individual surgeon's discretion) on the day after surgery as tolerated and discontinued at dismissal from hospital.

 Patients should be encouraged to maximize independent ambulation and increase distance ambulated daily

# Discharge Criteria

 Independent and safe using a walker or crutches for ambulation and satisfactory pain control.

# **Radiographic Parameters**

Standing alignment, lateral, and Merchant (45 degrees of flexion) radiographs will be obtained preoperatively, immediately postoperatively, and three months, two years, five years, seven years, and ten years after surgery. An independent reviewer will evaluate the radiographs for radiolucent lines, component position and alignment after all patients have completed the seven-year and ten-year visit.

### **Study Procedures**

Data Collection (obtained via a blinded research assistant)

Visit #1 Preoperative: Consent and initial data acquisition: Knee Society Clinical Rating Score, SF-12, Radiographs of the knee (standing alignment, lateral and Merchant view at 45° of knee flexion)

Visit #2 Three months: Radiographs of the knee (standing alignment, lateral and Merchant view at 45° of knee flexion); Knee Society Clinical Rating Score, SF-12. These questionnaires can be obtained in-office, by phone or by mail. While it is preferred that the visit occur in the clinic, if the participant is not returning they will still be asked to complete the study questionnaires.

Visit #3

Two years: As above #2. These questionnaires can be obtained inoffice, by phone or by mail. While it is preferred that the visit occur in the clinic, if the participant is not returning they will still be asked to complete the study questionnaires.

Visit #4

Five years: As above. These questionnaires can be obtained in-office, by phone or by mail. While it is preferred that the visit occur in the clinic, if the participant is not returning they will still be asked to complete the study questionnaires.

Visit #5

Seven years: As above. These questionnaires can be obtained in-office, by phone or by mail. While it is preferred that the visit occur in the clinic, if the participant is not returning they will still be asked to complete the study questionnaires.

Visit #7

Ten years: As above. These questionnaires can be obtained in-office, by phone or by mail. While it is preferred that the visit occur in the clinic, if the participant is not returning they will still be asked to complete the study questionnaires.

# **Measurement Tools**

# **Knee Society Clinical Rating Score**

This is a clinical standard for rating efficiency of total knee replacement. It is a disease-specific test, which has been validated and is widely used. These questionnaires can be obtained in-office, by phone or by mail. While it is preferred that the visit occur in the clinic, if the participant is not returning they will still be asked to complete the study questionnaires.

# **SF-12**

This self-administered questionnaire has been validated for measuring and monitoring health status in large group studies. These questionnaires can be obtained in-office, by phone or by mail. While it is preferred that the visit occur in the clinic, if the participant is not returning they will still be asked to complete the study questionnaires.

### **Complications/Lost to Follow-up Form**

Any serious complication, which occurs relating to the device, will be documented.

Sepsis, embolism, failure of primary wound healing, hemorrhage, prosthesis loosening, skin necrosis, hematoma, device failure or fracture are possible complications. If for any reason a patient is lost to follow-up (will not return for office visits or complete and return mailed study questionnaires) there must be a completed form to indicate this event.

#### **Financial Complications**

None

## **Timetable**

The estimated time required to enroll 572 cases is three years.

### **Medical Device**

All study devices are FDA-approved.

# PARTICIPANT POPULATION

# **Eligibility Criteria**

### **Inclusions:**

- 1. Subjects willing to sign the informed consent.
- 2. Subjects able to comply with follow-up requirements including postoperative weight bearing restrictions and self-evaluations.
- 3. Male and non-pregnant female subjects ages 21-85 years of age at the time of surgery.
- 4. Subjects requiring a primary total knee replacement.
- 5. Subjects with a diagnosis of osteoarthritis (OA), traumatic arthritis (TA), or avascular necrosis (AVN).
- 6. Subjects with intact collateral ligaments as determined by the surgeon investigator.

### **Exclusions:**

- 1. Subjects with inflammatory arthritis.
- 2. Subjects with a history of total or unicompartmental reconstruction of the affected joint.
- 3. Subjects that have had a high tibial osteotomy or femoral osteotomy.

- 4. Subjects with neuromuscular or neurosensory deficiency, which would limit the ability to assess the performance of the device.
- 5. Subjects with a systemic or metabolic disorder leading to progressive bone deterioration.
- 6. Subjects that are immunologically compromised, or receiving chronic steroids (>30 days).
- 7. Subjects bone stock is compromised by disease or infection that cannot provide adequate support and/or fixation to the prosthesis.
- 8. Subjects with knee fusion to the affected joint.
- Subjects with an active or suspected latent infection in or about the knee joint.
- 10. Subjects that are prisoners.

### Recruitment

The investigator or the research assistant will carry this out. The study will be described to the patient in detail, and a consent form, clearly stating the background and reasoning, will be given to the patient. A consent form will be signed by the patient and by a study person authorized to obtain consent. One copy will be go with the participant as stated, a second copy will go into the patient's medical record, and the original consent will be kept in the patient's study folder.

## Competency

Study participants must be able to give informed consent.

### Gender and Racial/Ethnic Distribution

No gender or racial/ethnic group will be intentionally excluded from this study.

#### **RISKS**

Participation in this study, involving FDA-approved devices, poses no increased risk to patients undergoing total knee replacement surgery. With any knee replacement, there is a possibility that the prosthesis will need to be removed and replaced and that the procedure may involve unforeseeable risks. Some of the known risks include: failure to achieve firm attachment of the implant to the bone, fracture of bone during implantation, infection, deep vein thrombosis, neurovascular injury, wound problems, extensor mechanism problems, and anesthetic problems. In a minority of cases, the knee prosthesis will loosen over years of use and pain and decreased mobility will occur.

#### STATISTICAL METHODS AND REVIEW STATEMENT

#### **Primary Efficacy Parameters**

The primary efficacy parameter is the revision rate for total knee arthroplasty. The key time point is ten years post-surgery.

### **Secondary Efficacy Parameters**

The secondary efficacy parameters include:

Active flexion, Passive flexion, Active extension, and Passive extension ROM at the 2, 5, 7 and 10-year visits.

KSS pain and motion scores at the 3 months, 2, 5, 7 and 10-year visit.

SF-12 scores at the 3 months, 2, 5, 7 and 10-year visit.

Radiographic success/failure at the 3 months, 2, 5, 7 and 10-year visits.

Radiographic failure is defined as a score of 10 or greater according to the Knee Society

Rotenographic Scoring System, regardless of symptoms. A migrating or shifting

prosthesis with or without the disappearance of radiolucent lines is also a failure

regardless of the score.

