**Secondary Efficacy Hypothesis** 

For the secondary efficacy parameters (when data is available), a non-inferiority

hypothesis will be tested at each scheduled follow-up visit, similar to the primary efficacy

hypothesis.

In addition, a comparison of the scores at each post-surgery visit with baseline (i.e.,

improvement scores) will be tested to see if any improvement is seen for each parameter

and time point.

For categorical secondary parameters (i.e., radiographic success/failure, subsidence and

radiolucency), the non-inferiority alternative hypothesis is that the risk in the X3

polyethylene group is not  $\Delta_0$ % worse relative to the N2Vac treated group within the

period from surgery to the scheduled follow-up visit. Formally the non-inferiority null

and alternative hypotheses are:

 $H_{NI,O}$ :  $\pi_{X3}/\pi_{N2Vac} > \Delta_0$ , and

 $H_{NI,A}$ :  $\pi_{X3}/\pi_{N2Vac} < \Delta_0$ , where  $\pi_{X3}$  is the rate in the Triathlon CR Total Knee

System group using the X3 polyethylene,  $\pi_{N2Vac}$  is the rate in the Triathlon CR

Total Knee System group using the N2Vac, and  $\Delta_0$  is the equivalence limit

difference ( $\Delta_0$ ).

For continuous secondary parameters (i.e., ROM, KSS, SF12), the non-inferiority

alternative hypothesis is that the mean using the X3 polyethylene is not  $\Delta_0$  worse than the

mean using the N2Vac treated group within ten years. Formally the non-inferiority null

and alternative hypotheses are:

 $H_{NI,O}$ :  $\mu_{X3} \ge \mu_{N2Vac} + \Delta_0$ , and

 $H_{NI,A}$ :  $\mu_{X3} < \mu_{N2Vac} + \Delta_0$ , where  $\mu_{X3}$  is the mean in the Triathlon CR Total Knee System group using the X3 polyethylene,  $\mu_{N2Vac}$  is the mean in the Triathlon CR Total Knee System group using the N2Vac, and  $\Delta_0$  is the equivalence limit difference ( $\Delta_0$ )..

The equivalence limit differences are as follows.:

Parameter	Equivalence Limit Difference ( $\Delta_0$ )
Range of Motion (ROM)	10 degrees
KSS pain and motion	10%
SF-12	10%
Radiographic success/failure	No complete radiolucent lines
Subsidence and Radiolucency	No component subsidence

In addition, for the continuous parameters, a comparison of the scores at each postsurgery visit with baseline (i.e., improvement scores) will be tested to see if any improvement is seen for each parameter at each time point. That is, the formal hypothesis to be tested is that the difference is zero. This is tested by:

$$H_{I,O}$$

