# **Efficacy Analyses**

#### Methods

Primary Parameter: The relative risk of revision (X3 relative to N2Vac) at ten years will be computed and a 95% confidence interval on the rate ratio computed, assuming a Poisson distribution. If the upper end of the confidence interval for the rate ratio is less than 1.0, then the superiority hypothesis will be supported. Otherwise, if the upper end of the confidence interval is less than 1.2, then the non-inferiority hypothesis will be supported. Secondary Parameters: The categorical secondary efficacy parameters will be analyzed at each nominal visit by computing the 95% confidence interval for the rate ratio (relative risk) of the groups as above. The clinically significant difference ( $\Delta_0$ ) is as presented on page 13 above. The continuous secondary efficacy parameters will be analyzed at each nominal visit. The 95% confidence interval on the difference between the two groups will be computed using the means, t-distribution and appropriate standard deviation. The change from baseline will also be presented and their 95% confidence interval and p-value for the paired t-test using the baseline will be presented for each nominal visit and treatment group, along with the descriptive statistics.

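### The margin table puts a per-knee radiographic criterion where a rate-ratio margin belongs, and for radiographic success/failure that criterion conflicts with the plan's only definition of failure

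*Combined protocol and SAP*

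**What the plan says.** **The definition.** Secondary Efficacy Parameters lists radiographic success/failure at three months and at two, five, seven and ten years. Its definition has two limbs. The first rests on a score: "Radiographic failure is defined as a score of 10 or greater according to the Knee Society" system for reading films, and symptoms play no part. The second covers implants that migrate or shift. It says in part "prosthesis with or without the disappearance of radiolucent lines is also a failure", and it applies whatever the score. Nothing else in the document is labelled a definition of radiographic failure.

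**The hypothesis.** Secondary Efficacy Hypothesis opens the categorical case with "For categorical secondary parameters (i.e., radiographic success/failure, subsidence and" and goes on to radiolucency. It tests the X3/N2Vac ratio for each against a limit Δ0.

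**The margin table.** It is introduced by "The equivalence limit differences are as follows". Beside radiographic success/failure the entry is "No complete radiolucent lines". Beside subsidence and radiolucency it is "No component subsidence".

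**The analysis.** Methods, under Efficacy Analyses, plans a 95% confidence interval for the rate ratio at each visit and takes the clinically significant difference from that table.

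**The reading of films.** Radiographic Parameters has an independent reviewer assess radiolucent lines, component position and alignment, once all patients have completed the seven-year and ten-year visits. It mentions neither the score nor migration.

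**The concern.** A non-inferiority margin for a rate ratio has to be a number. The two categorical entries are descriptions of a single knee, so they make sense only as success criteria. The one beside radiographic success/failure uses a different feature of the film (a complete radiolucent line) from the definition (score, or migration). The table also has a row for subsidence, which the list of secondary parameters does not mention, and the plan does not say whether subsidence is part of what the definition calls migrating or shifting.

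An analyst who follows Methods back to the table finds no usable margin and a text that can be taken for a different event rule. The independent reading comes late and its description omits the two items the definition needs. The choice of rule could therefore be made after the films have been read, for a named secondary endpoint tested at five visits.

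**Working it through.** The plan gives no radiographic rate, so there is no figure to reproduce. The main check is a comparison of the texts.

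**Step 1. Can the entries be margins?** The hypothesis compares π(X3)/π(N2Vac) with Δ0. The primary hypothesis shows the form required: a ratio limit of 1.2. The two categorical entries contain no number. As the table stands, the test cannot be carried out.

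**Step 2. If the first entry is read as a criterion, does it agree with the definition?** The definition fails a knee if the score is 10 or more or the prosthesis migrates. The entry, so read, fails a knee if there is a complete line.

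| Score ≥10 | Migrating | Complete line | Definition | Table entry | Agree? |
|---|---|---|---|---|---|
| no | no | no | success | success | yes |
| no | no | yes | success | failure | **no (a)** |
| no | yes | no | failure | success | **no (b)** |
| no | yes | yes | failure | failure | yes |
| yes | no | no | failure | success | **no (c)** |
| yes | no | yes | failure | failure | yes |
| yes | yes | no | failure | success | **no (d)** |
| yes | yes | yes | failure | failure | yes |

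Four of the eight combinations conflict. Case (b) follows from the definition's own words: migration counts whatever the score, and the definition allows for lines having disappeared. Cases (a), (c) and (d) assume that the score can fall on either side of 10 independently of a complete line. The scoring rules are not in the documents, so those three remain conditional.

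**Step 3. Illustration of size (assumed rates).**
- Knees per arm at ten years: 286 × 0.90 = 257.4, from the Sample Size Justification.
- Assumed: failure by the definition in 5% of N2Vac knees, of which 1.5 points are migration without a complete line; the other 3.5 points all show a complete line.
- Assumed: a further L = 2%, 5% or 10% of knees with a complete line but no failure by the definition, equal in both arms. This needs case (a) to be possible.
- Definition: N2Vac events = 257.4 × 0.05 = 12.9; X3 events = 12.9 × RR.
- Table criterion: N2Vac events = 257.4 × (0.035 + L); X3 events = 257.4 × (0.035 × RR + L).
- Interval: ratio × exp(±1.96 × SE), with SE = √(1/events X3 + 1/events N2Vac).

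| True RR | Rule | X3 v N2Vac events | Ratio (95% CI) |
|---|---|---|---|
| 0.32 | definition | 4.1 v 12.9 | 0.32 (0.11–0.97) |
| 0.32 | table, L = 2% | 8.0 v 14.2 | 0.57 (0.24–1.35) |
| 0.32 | table, L = 5% | 15.8 v 21.9 | 0.72 (0.38–1.38) |
| 0.32 | table, L = 10% | 28.6 v 34.7 | 0.82 (0.50–1.35) |
| 2.0 | definition | 25.7 v 12.9 | 2.00 (1.02–3.91) |
| 2.0 | table, L = 2% | 23.2 v 14.2 | 1.64 (0.84–3.17) |
| 2.0 | table, L = 5% | 30.9 v 21.9 | 1.41 (0.82–2.44) |
| 2.0 | table, L = 10% | 43.8 v 34.7 | 1.26 (0.81–1.97) |

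At a true ratio of 0.5 the definition itself gives 6.4 v 12.9 events and 0.50 (0.19–1.29), which already includes 1. The illustration therefore says nothing about a halving.

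**Step 4. Effect on a non-inferiority claim.** No categorical margin is given, so I borrow the primary limit of 1.2 as an assumption. The chance that the upper limit falls below it is Φ[(ln 1.2 − ln ratio)/SE − 1.96]. At a true ratio of 2.0 this is 0.03% under the definition and 0.2% to 1.5% under the table criterion. At 0.32 the expected upper limit rises from 0.97 to between 1.35 and 1.38, so the claim becomes harder.

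**The case against.** The strongest answer is that the documents define failure once. The table is introduced and headed as a list of margins, no sentence says that an entry redefines the event, and Methods cites the table only for the clinically significant difference. A reader might infer that the plan holds two rival event definitions. The documents do not support that: there is one labelled definition and, in the margin column, a misplaced text that conflicts with it once it is read in the only way that gives it meaning. This part of the objection stands and limits the point. It does not remove it, because the texts cannot work as margins and no section says how they relate to the definition.

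The table may also be misaligned in the text read from the PDF: the two entries together would fit the single row for subsidence and radiolucency. That cannot be settled from the text. If it is so, the conflict in case (b) disappears, but the radiographic success/failure row then has no limit and the other row still has no numeric one.

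A reader might further infer that the table takes subsidence, or migrated components, out of the failure endpoint. The plan names subsidence as a parameter of its own and never equates it with migrating or shifting, so that reading goes too far.

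Finally, the dilution in the illustration is produced by its inputs: every rate is assumed, and equal line rates in the two arms are assumed too. That is right, and the figures show direction only.

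**Conclusion.** The point holds in a limited form. The margin column carries per-knee criteria in place of numbers for the categorical endpoints. One of them, read as a criterion, conflicts with the stated definition in at least one case that follows from the definition's own wording: a migrating prosthesis with a score below 10 and no complete line. The other three conflicts depend on scoring rules outside the documents.

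The effect on results cannot be sized from the documents. The illustrative attenuation (0.32 to 0.57–0.82; 2.0 to 1.64–1.26) rests on assumed rates and applies to those two true ratios only.

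A reader might infer that the looser wording makes non-inferiority easier to claim. That is not supported: no margin exists, and with 1.2 borrowed the chance at a true ratio of 2.0 stays at or below 1.5%, while at 0.32 the claim becomes harder.

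This is a secondary endpoint and the primary analysis of revision is untouched. It should still be corrected, because the planned test cannot be run as written and the event rule should be fixed before the films are read.

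**What to change.** 1. In Secondary Efficacy Hypothesis and in Methods, state that the definition in Secondary Efficacy Parameters is the sole event rule for radiographic success/failure.
2. Remove the two descriptive texts from the margin column. Put a prespecified numeric rate-ratio margin in each cell, or state that these endpoints are reported with a 95% confidence interval and without a non-inferiority claim.
3. State whether subsidence and radiolucency are separate endpoints or components of the failure composite. Either is workable; the plan has to say which.
4. Under Radiographic Parameters, have the existing independent reviewer's form record the score and any migration, so that the definition can be applied to each film.

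The cost is wording in those sections and two items on a form. No new films, patients or readers are needed.
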